2.1. PRIMARY OUTCOMES

1. Pain (Difference between preoperative and postoperative EVA (24 hours, 10-15 days after surgery, 1 month after surgery))
 - a. Analgesia intake
2. Swelling (difference with healthy limb and difference between preoperative and postoperative (24 hours, 10-15 days after surgery, 1 month after surgery))
3. Patient satisfaction (Scale 1-5 and questionnaire)

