Is WALANT Applicable in Distal Radius Fracture Osteosynthesis?

Study Protocol and Statistical Analysis Plan

October 2020

NCT (still not available)

ABSTRACT

Title → Is WALANT Applicable in Distal Radius Fracture Osteosynthesis?

Aims → To evaluate is Wide Awake Local Anaesthesia No Tourniquet (WALANT) is applicable to distal radius fracture (DRF) osteosynthesis and possible benefits of not using the ischemia cuff in distal radius osteosynthesis, by using the WALANT anaesthetic technique and compare it with patients who have undergone the current anaesthesia method (locoregional anaesthesia with or without sedation)

Material and methods → Randomized controlled study comparing patients operated on for distal radius fracture with osteosynthesis during a year (December 2020 to December 2021). The randomization will be done by 10 block in order to ensure similar numbers of patients in both groups of intervention. In the group A patients will be operated on with local anaesthesia (lidocaïne + adrenaline + bicarbonate) with or without sedation without the use of ischemia, while in group B patients will be given anaesthesia by proximal locoregional blockade with or without sedation and ischemia cuff. Immediate short-term results will be compared between both groups. Primary outcomes will be preoperative and postoperative pain, pre and postoperative swelling, and patient and surgeon satisfaction.

Results →

Conclusion →

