3.3. VARIABLES

Independent variables:

These variables will be collected during the surgery and in the subsequent from patient anamnesis, clinic history and filling the Collection Data Guide Form:

- Age (years)
- Sex (male / female)
- Dominant hand (left / right / both)
- Injured hand (left / right / two)
- Fracture classification according to American Orthopaedic (AO) (16), (17)
- Number of days from injury to surgery (days)
- Preoperative pain (VAS scale (18))
- Preoperative swelling injured hand and healthy hand. The perimeter of the wrist will be measured at the height of the proximal palmar fold in cm.

Dependent variables:

These variables are the ones we want to study and will be collected during the surgery and afterwards from patient anamnesis, clinic history and filling the Collection Data Guide Form:

- Duration of admission (hours).
- Duration of surgery (minutes).
- Duration of ischemia in group B (minutes).

- Preoperative and postoperative pain (VAS scale): Pain at baseline, 24 hours post-intervention, at the visit of the first treatment 10-15 days post-intervention and pain 1 month after the intervention.
- Intraoperative pain (VAS scale): Assessable only if it has not required sedation.
- Time (minutes) of anaesthesia administration
- Time (minutes) from the end of administration to the beginning of IQ
- Need for anaesthetic reinforcement:
 - Sedations (yes/no) and reason
 - In the case of WALANT: Taking into account the reference technique used (10), if any extra doses are needed and location within the wrist
- Postoperative analgesia during admission and discharge (drugs used, dose and frequency of use)
- Postoperative swelling injured hand and healthy hand (cm).
- Stained dressing and the presence of active bleeding due to the wound within 24 hours and during the first outpatient clinic 10 or 15 days after surgery.
- Patient satisfaction during the first outpatient clinic 10 or 15 days after surgery. → Assess satisfaction (1-5) / Would you repeat the anaesthesia type? / Would you recommend the technique?
- Description of the complications of anaesthesia.
- Description of postoperative complications.
- Mobility 24 hours post-intervention, first aid and one month later. (The mobility of the fingers, intrinsic and extrinsic muscles, Kapandji exercises 1-10 and wrist mobility will be assessed by measuring flexion-extension and prone-supination with a goniometer).
- Surgeon's experience

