3.5 LIMITATIONS OF THE STUDY

- The sample size (N) may be small.
- VAS scale is a subjective measure and therefore makes it difficult to compare different patients. However, to date, there are no objective pain assessment scales that meet this purpose.

- The doses of anaesthesia used in the proximal block will not be the same in all patients and depend on the anaestheologist in charge of the operating room in that moment.

- Heterogeneity of fractures may vary the results of the study, as more complex fractures can cause more pain.

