3.6 STATISTICAL PLAN

Quantitative values will be described as mean and standard deviation in case of normal distribution, or with median and interquartile range otherwise. Qualitative variables will be described with absolute and relative frequencies. The Student's t test for normal quantitative variables and the non-parametric Mann-Whitney U test will be used to compare the two experimental groups. Pearson's chi-square test for expected frequencies above 5 and Fisher's exact test would be used to compare the distribution of qualitative variables between groups. Statistical program R [ref] will be used, applying a statistical significance level of 5%.

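### Primary swelling is listed as two differences with no rule for combining them, and neither is compared between arms with adjustment for the preoperative side difference, which is collected; the cost is precision, not validity

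*Combined protocol and SAP*

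**What the plan says.** Section 2.1, item 2, defines the primary swelling outcome as "Swelling (difference with healthy limb and difference between preoperative and postoperative (24 hours, 10-15 days after surgery, 1 month after surgery". Two differences are joined by a single conjunction and followed at three visits. The item does not say whether they are two endpoints or one measure (the side difference followed from before to after surgery), and it names neither as decisive.

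Section 3.3 lists "Preoperative swelling injured hand and healthy hand" among the independent variables and "Postoperative swelling injured hand and healthy hand (cm" among the dependent variables. Both limbs are therefore measured before and after the operation.

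Section 3.6 gives one rule for quantitative outcomes: "The Student's t test for normal quantitative variables and the non-parametric Mann-Whitney U test will be used to compare the two experimental groups", "applying a statistical significance level of 5" per cent. It names no regression, covariate or repeated-measures model.

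The abstract describes allocation so: "The randomization will be done by 10 block in order to ensure similar numbers of patients in both groups of intervention". No stratification is described. The only remark on sample size is in the limitations (section 3.5): "The sample size (N) may be small".

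**The concern.** Less swelling is one of the two benefits in the study hypothesis, and swelling is a primary outcome. Two weaknesses meet here.

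- **Definition.** If the two differences are separate contrasts, they can give different answers in the same trial. When the arms differ by chance in preoperative swelling, a postoperative side difference carries that imbalance in full, while a pre-to-post difference subtracts it in full. The plan does not say which would then decide.
- **Efficiency.** A postoperative-only comparison leaves all between-patient variation in preoperative swelling in the error term. A change score removes it with a fixed coefficient of one, which over-corrects when the correlation is modest. Regression on the preoperative value estimates that coefficient. With equal standard deviations before and after surgery it is, apart from the one degree of freedom spent, at least as precise as either.

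In a trial whose authors expect that numbers may be small, this precision is worth having, because the covariate is already on the data form.

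**Working it through.** **Inputs from the documents.** Two-arm comparison; arms of similar size (1:1 assumed); significance level 5% (two-sided assumed, since sidedness is not stated); perimeters of both limbs before and after surgery. The plan states no sample size, power, effect, standard deviation or correlation, so it has no figure of its own to reproduce.

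**Assumptions.** Equal standard deviation (set to 1) of the side difference before and after surgery; pre/post correlation ρ of 0.3, 0.5 or 0.7; true effect of 0.5 SD; normal approximation.

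**Step 1: what each contrast does with baseline.** If the healthy limb does not change, (injured post − healthy) − (injured pre − healthy) = injured post − injured pre. The pre-to-post difference in section 2.1 is then the same as a change in side difference, and the healthy limb cancels. Only two unadjusted forms need comparing: postoperative-only and change.

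**Step 2: residual variance.**

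- Postoperative-only: 1
- Change: 2(1 − ρ)
- Analysis of covariance (ANCOVA): 1 − ρ²

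Relative to ANCOVA, postoperative-only is 1/(1 − ρ²), and change is 2(1 − ρ)/(1 − ρ²) = 2/(1 + ρ).

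| ρ | Post-only ÷ ANCOVA | Change ÷ ANCOVA |
|---|---|---|
| 0.3 | 1/0.91 = 1.10 | 2/1.3 = 1.54 |
| 0.5 | 1/0.75 = 1.33 | 2/1.5 = 1.33 |
| 0.7 | 1/0.51 = 1.96 | 2/1.7 = 1.18 |

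At ρ = 0.5 both unadjusted forms need one third more patients than ANCOVA. Below 0.5 the change score is the worse of the two; above 0.5 postoperative-only is.

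**Step 3: power.** A postoperative-only comparison needs 63 per arm for 80% power at 0.5 SD. With 63 per arm:

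| ρ | Post-only | Change | ANCOVA | Gain over the better unadjusted form |
|---|---|---|---|---|
| 0.3 | 80.1% | 66.0% | 83.7% | 83.7 − 80.1 = 3.6 points |
| 0.5 | 80.1% | 80.1% | 90.0% | 90.0 − 80.1 = 9.9 points |
| 0.7 | 80.1% | 95.2% | 97.6% | 97.6 − 95.2 = 2.4 points |

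For 80% power, ANCOVA needs 58, 48 and 33 per arm at these correlations, and the change score needs 88, 63 and 38.

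With 30 per arm and the same effect, postoperative-only has 49.1% power. Change has 37.3%, 49.1% and 70.5%, and ANCOVA has 52.8%, 60.9% and 77.4%. The gains over the better unadjusted form are 3.7, 11.8 and 6.9 points.

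**Step 4: disagreement, if the two are separate contrasts.** The correlation between the two estimates is (1 − ρ)/√(2(1 − ρ)) = √((1 − ρ)/2), that is 0.59, 0.50 and 0.39. With 63 per arm and 0.5 SD, exactly one of the two is significant in about 27%, 23% and 20% of trials. With 30 per arm and 0.6 SD the figure is 31% to 33%.

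**The case against.** The strongest reply is that the plan does not ignore baseline. The same item names the pre-to-post difference, which already removes preoperative swelling if the healthy limb is stable. A reader might infer that the healthy-limb difference is a postoperative value only, and that preoperative swelling is therefore disregarded. The text does not say so: the wording can also mean the side difference followed from before to after surgery, and the abstract names swelling before and after surgery together. This part of the objection stands.

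A second reply concerns size. At ρ = 0.7, measuring ANCOVA against the postoperative-only form alone suggests a gain of 97.6 − 80.1 = 17.5 points. Because the plan also names the change, the fair comparator there is the change score, and the gain is 2.4 points. That also stands, and it is why the gains above are taken against the better unadjusted form.

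Third, every numerical input is assumed, and one correlation need not hold at 24 hours, 10-15 days and one month. This is true; the figures show a range and are not estimates for this trial.

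Fourth, the injured-hand field in section 3.3 allows both hands to be coded. Such a patient has no healthy limb, so an endpoint built on the side difference needs an exception.

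None of this removes the central point. Under either reading section 3.6 contains no baseline-adjusted comparison, and under either reading ANCOVA does at least as well.

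**Conclusion.** The point holds as one of precision and clarity. Primary swelling is ambiguously defined, and the plan leaves unused a covariate that it collects. The gain over the better unadjusted contrast is about 4, 10 and 2 points of power at correlations of 0.3, 0.5 and 0.7, starting from 80% for the postoperative-only form. It is largest near 0.5, where the two unadjusted forms are equally good. These figures rest on equal standard deviations before and after surgery, 1:1 allocation, a two-sided 5% level and a normal approximation.

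A reader might go further and infer bias or an invalid test. The documents do not support that: in a randomised comparison the unadjusted tests keep their validity, and a chance imbalance in preoperative swelling adds error, not systematic bias. The change is worth making because it costs almost nothing and also settles which swelling contrast decides at each visit. The lack of one decisive visit among the three is a separate matter, which this change does not resolve.

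**What to change.** In section 2.1, define one swelling endpoint per visit: the postoperative injured-minus-healthy perimeter in cm.

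In section 3.6, state that it is analysed by linear regression on arm with the preoperative injured-minus-healthy perimeter as covariate, and that the adjusted mean difference is reported in cm with a 95% confidence interval. This replaces the unadjusted swelling comparisons as the deciding analysis. Report the raw pre-to-post change as supportive.

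Add a rule for patients with both hands injured. Either leave them out of this endpoint and say so, or use the postoperative injured perimeter adjusted for the preoperative injured perimeter.

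The cost is a few sentences and one regression per visit on measurements already collected. The downsides are one degree of freedom, a linearity assumption and the small exception for patients with both hands injured.

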2.2. SECONDARY OUTCOMES

1. Evolution of the surgical wound (active bleeding and dressing condition at 24 hours and 10-15 days after surgery)
2. Postoperative mobility
 - a. Thumb mobility and opposition (Kapandji scale)
 - b. Finger mobility (capability of the patient to arrive at proximal and distal palm crease)
 - c. Wrist mobility (flexion, extension, pronation, supination, ulnar deviation, radial deviation)
3. Surgeon's technical difficulty.
 - a. Scale 1-5 (1 easy- 5 difficult)
 - b. Intraoperative stress /yes/no) and reason
4. Insufficient anaesthesia
 - a. Need of change to General Anaesthesia
 - b. Need of adding more anaesthesia
 - i. Type of anaesthesia used (sedation, local anaesthesia reinforcement, etc.)

- ii. Reason for change
- 5. Postoperative complications (total number and description)

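### Finger mobility is defined only by reaching two palm creases; recording the fingertip-to-crease distance would keep information that the plan discards, at little cost

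*Combined protocol and SAP*

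**What the plan says.** All references are to the combined protocol and SAP.

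- **Definition.** Section 2.2 lists postoperative mobility as a secondary outcome, with thumb, finger and wrist sub-items. The finger sub-item reads "Finger mobility (capability of the patient to arrive at proximal and distal palm crease". No unit, scoring rule or choice of finger is given.
- **Measurement.** Section 3.3 states: "The mobility of the fingers, intrinsic and extrinsic muscles, Kapandji exercises 1-10 and wrist mobility will be assessed". The sentence goes on to name a goniometer, which most naturally belongs to the wrist. No distance or angle is named for the fingers.
- **Timing.** Section 3.3 gives "Mobility 24 hours post-intervention, first aid and one month later". The middle visit is read here as the 10-15 day check-up. No single visit is singled out for finger mobility.
- **Analysis.** Section 3.6 sends categorical items to chi-square or Fisher: "Pearson's chi-square test for expected frequencies above 5 and Fisher's exact test would be used to compare the distribution of qualitative variables between groups". For quantitative variables it names the t test, and the "non-parametric Mann-Whitney U test will be used to compare the two experimental groups". The level is 5%, without a stated sidedness.
- **Size.** No sample size, power, effect, standard deviation or expected share reaching a crease is stated for any outcome. The limitations section concedes that N could turn out small.

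**The concern.** Reaching or not reaching a landmark is a coarse cut of a quantity that can be measured in centimetres. The neighbouring mobility items keep more detail: the thumb has the Kapandji scale (1-10), and wrist movement is measured with a goniometer. For the fingers, the available text keeps only which of two creases was reached and gives no reason for stopping there.

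The hypothesis in the introduction includes leaving short-term results unaltered. A coarse outcome in a trial that may be small leans towards a non-significant comparison, which could then be read as support for that part of the hypothesis. If the two creases are tested separately at the three mobility visits, there are also 2 × 3 = 6 tests where a single distance would need 3.

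**Working it through.** **1. The plan's own figure.** There is none to reproduce, because the plan contains no power calculation.

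**2. Inputs.** From the documents: the two creases (2.2), the test rule and the 5% level (3.6), and roughly equal arms (blocks of 10, abstract). Assumed: two-sided testing; 30 or 50 per arm; normally distributed finger reach with SD 1; a true shift of 0.6 SD; distance floored at 0 when the harder crease is reached and recorded in steps of 0.25 SD; the other crease 0.5 or 1 SD easier; no dropout.

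**3. Hand check, 30 per arm, 10% of the comparison arm reaching the harder crease.** The threshold is z = 1.2816.

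- Crease 1 SD easier: shares are 1 − Φ(0.2816) = 0.389 and 1 − Φ(0.2816 − 0.6) = 0.625, a difference of 0.236. The pooled standard error is √(2 × 0.507 × 0.493/30) = 0.129. The unpooled one is √((0.389 × 0.611 + 0.625 × 0.375)/30) = 0.125. Power ≈ Φ((0.236 − 1.96 × 0.129)/0.125) ≈ 45%.
- Crease 0.5 SD easier: shares are 0.217 and 0.428, and the same formula gives about 41%.
- Full distance, t test without a floor: Φ(0.6 × √(30/2) − 1.96) = Φ(0.364) ≈ 64%. Using Mann-Whitney with the floor and rounding brings this to about 60% in simulation.

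**4. Simulation with the section 3.6 rule** (chi-square if all expected counts exceed 5, otherwise Fisher). The crease column takes whichever single crease has the higher power. That favours the plan, since the better crease is not known in advance. It is not the chance that either crease is significant; that chance is higher, but such a rule can push the false-positive rate above 5%.

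| Per arm | Comparison arm reaching harder crease | Better crease test | Mann-Whitney on distance | Loss (points) |
|---|---|---|---|---|
| 30 | 10% | 42-46% | 60-61% | 14-19 |
| 50 | 10% | 63-71% | 82-83% | 11-20 |
| 30 | 20% | 41-47% | 57-58% | 10-17 |
| 30 | 30% | 45-46% | 54-55% | 8-10 |
| 50 | 30% | 66-67% | 78% | 11-12 |
| 30 | 50% | 45% | 49-50% | 4-5 |
| 50 | 50% | 65% | 70% | 5 |

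Ranges cover the two assumed gaps between creases. Losses subtract the ends of the ranges, which slightly widens the spread; paired within a scenario, the 10% rows give about 12-20 points. At 70% reaching, the loss is about 1-5 points. Under no true difference, Mann-Whitney rejected in 4-5% of trials. With 2,000 to 3,000 trials per setting, the simulation standard error of a power figure is at most √(0.25/2000) = 1.1 points.

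**5. If both creases form one ordered score (neither, one, both).** In the model above, Mann-Whitney on this score gains mostly 1-7 points, and at most about 12, over the better crease test. A second model set the shift to 2.80 × √(2/n), which gives 80% power for a t test on the unfloored distance, with 20-50 per arm and the easier crease reached by 30 percentage points more of the comparison arm. The ordered score then loses about 9-12 points against distance at 5% reaching, 6-9 at 10%, 3-6 at 20% and 2-3 at 30-50%. A single crease in the same model loses 52-60, 31-37, 15-19, 10-12 and 4-6 points at 5, 10, 20, 30 and 50%.

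**6. Reading.** The direction is the same throughout. The size depends on the scoring and on the share reaching the creases, and the documents give neither.

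**The case against.** The strongest case against is that the scoring is undefined rather than wrong.

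- **Yes/no is an inference.** Section 2.2 marks surgeon stress as yes/no but does not do so here, and two ordered landmarks fit a three-level score equally well. This stands. It reduces the loss but does not remove it, because the ordered score still ignores how far short a patient falls. It is also not written into the plan.
- **The detail may be on the data collection form**, which is not in the available text, and the goniometer sentence does not strictly exclude the fingers. This stands as a caveat. A sponsor whose form already holds a finger measurement need only bring 2.2 and 3.6 into line with it.
- **A reader might infer that few patients can reach the palm, or that nearly all fail at 24 hours.** The documents give no rate at any visit. If half or more reach the harder crease, the loss is about 5 points or less under the 0.6 SD assumptions.
- **A reader might infer that a patient just short of a crease and one several centimetres short always count alike.** That holds for a single crease. With two creases they count alike only if both also miss, or both reach, the other one.
- **It is a minor item.** Finger mobility sits beside Kapandji and six wrist movements among the secondary outcomes. This stands, and it limits the point to a low-cost improvement.

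**Conclusion.** The point holds in a limited form. In the available text the finger outcome is at most two binary items or a three-level score, and it discards the remaining distance.

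The working puts the cost of separate crease tests between about 1 and 20 points of power, falling as more patients reach the harder crease. Those figures rest wholly on the assumed arm size, shift, normal distribution and reach rates. A reader might take one range as a property of this trial; the documents do not support that, since changing the assumed effect and scoring moved the loss from about 2 points to about 60.

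The calculation also takes distance to the harder crease, and the documents do not say which crease that is. If it is the proximal one, a distance to the distal crease would reach its floor sooner and the gain would be smaller.

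Nothing here bears on pain, swelling or patient satisfaction, the primary outcomes in section 2.1.

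**What to change.** In section 2.2, item 2b, and on the data form, record the fingertip-to-distal-palm-crease distance in cm (0 = reached), for example for the worst finger, at the mobility visits already planned. State in section 3.6 that groups are compared with Mann-Whitney on that distance, and report the two crease items as descriptive percentages only.

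If the form cannot change, state that the two creases are analysed as one ordered score (neither, one, both) with Mann-Whitney, instead of two separate chi-square or Fisher tests. This needs no new data.

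The cost is one short ruler reading and one form field per visit, plus one sentence in the plan. No visit, patient or treatment changes. The drawback is that a median distance is slightly less direct to read than a percentage, and the retained crease percentages answer that.
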